This protocol has no related submissions (RSC, GCRC, IBC, etc)

2 **Required Department and Specialty Reviews** - Based on the PI's organization (department, division, etc.) affiliation and answers to previous questions (use of Cancer Center, etc.), the organizations listed below are required to review this application. These reviews are conducted online and no additional forms or steps by the study team are required.

Name of Organization

Neu Multiple Sclerosis

Review Status

Complete

ID: VIEW4E1C8D9AE4000

Name: v2_Summary of Required Reviews (other than IRB)

Additional Documents

1 Upload all additional documents here:

Name	Created	Modified Date
HP-00060526-Mod23-PO_and_ISSO_signed_checklist.pdf(0.01)	1/25/2019 4:15 PM	1/25/2019 4:15 PM
TeleBATRAC_Study_Flowsheet_MHV-20190115.docx(0.02)	12/17/2018 12:19 PM	1/15/2019 2:35 PM
New Informed Consent and HIPAA Quality Checklist - Revised 11.5.2018(0.01)	11/28/2018 2:16 PM	11/28/2018 2:16 PM
16.07.20 I-SMB policy.doc(0.01)	10/15/2018 9:48 AM	10/15/2018 9:48 AM
FINAL MINTUES MERCE Safety Monitoring Board Meeting MINUTES Nov 2017(0.01)	3/5/2018 3:34 PM	3/5/2018 3:34 PM
VA_ISO_PO_Checklist.pdf(0.01)	1/26/2018 12:19 PM	1/26/2018 12:19 PM
VA_ISO_PO_Checklist_edits.docx(0.01)	1/23/2018 3:32 PM	1/23/2018 3:32 PM
MyHealtheVet_Forgot User ID Info(0.01)	5/2/2017 8:18 AM	5/2/2017 8:18 AM
MyHealtheVet Patient Handbook(0.01)	5/2/2017 8:16 AM	5/2/2017 8:16 AM
KinArm_ISO_Certificate(0.01)	3/28/2017 8:10 AM	3/28/2017 8:10 AM
KinArm Robot_User Guide(0.01)	3/24/2017 2:14 PM	3/24/2017 2:14 PM
Response_MRSA_Jan.2016(0.01)	1/26/2016 11:49 AM	1/26/2016 11:49 AM
Evaluation to Sign the Informed Consent(0.03)	12/11/2015 2:08 PM	12/15/2015 1:19 PM

ID: VIEW4E0962513A000
Name: v2_Additional Documents

Final Page of Application

You have reached the final page of this application. It is recommended that you click on the "Hide/Show Errors" link on the upper or lower breadcrumb row of this page. The "Hide/Show Errors" will do a search of your application, and highlight areas that are required or need to be completed prior to submitting.

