 Novel_Robotic-Task_Bimanual_Assesment_Lowrey2014(0.01)	3/21/2017 10:03 AM	3/21/2017 10:03 AM
 References_MyHealtheVet SECURE MESSAGING PILOT STUDY(0.01)	10/3/2016 11:45 AM	10/3/2016 11:45 AM
 References from Grant Submission(0.01)	10/1/2015 1:39 PM	10/1/2015 1:39 PM
 Coupar et al. 2012_Home Based Therapy_Cochrane Review(0.01)	7/10/2014 11:53 AM	7/10/2014 11:53 AM
 Duncan et. al 2011_Body Weight Support TM_NEJM(0.01)	7/10/2014 11:52 AM	7/10/2014 11:52 AM
 Fearon et al. 2012_Early Supported Discharge_Cochrane Review(0.01)	7/10/2014 11:51 AM	7/10/2014 11:51 AM

ID: VIEW4E02805A7E400
Name: v2_Supporting Literature

Study Procedures

If you uploaded a separate research protocol document in the 'Research Protocol' page, cite the applicable section and page numbers from that document in the answer boxes below. (If this study is a collaborative UM/VA study please list each procedure that is being conducted and the locations where it is being conducted.)

1 * Describe all procedures being performed for research purposes only (these procedures would not be done if individuals were not in the study) and when they are performed, including procedures being performed to monitor subjects for safety or to minimize risks:

A) General Medical Evaluation: A general neurological evaluation will be conducted at baseline by a neurologist to confirm clinical diagnosis of stroke and review medical records relating to the index stroke. It also includes a review of questionnaires specific to depression and neurocognitive function (Center for Epidemiologic Studies Depression Scale [CESD] and Montreal Cognitive Assessment [MoCA]). Clinical suspicion or evidence on the CESD and MoCA of dementia, depression, severe aphasia,, or other major neuro-cognitive deficits that may interfere with the conduct of the study preclude further evaluation and initiate prompt referral to psychiatry or other specialist for evaluation.

B) Evaluations of Arm Function and Use: These will be performed at the VA by an evaluator blinded to treatment allocation and will occur three times at baseline, at final training (week 6-9), and after an 8 week no training retention period.

C) Questionnaires about arm use and participation will also be completed. The research evaluations are as follows below.

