Robotic Bimanual Coordination Evaluation: The KinArm robot, a clinical arm robot designed to assess post-stroke sensorimotor deficits and quantify bilateral arm movements will be used to examine arm kinesthesia and bimanual impairment. The robot evaluation will be performed in a seated position with each arm supported by the robot exoskeleton. Participants will be prompted by a visual target or be moved by the robot to mirror-match arm positions within a horizontal plane of motion. The robot will record and store all movement data. Safety will be ensured with a study staff member present at all times. The robot also has an emergency stop system built in for quick termination of any testing if necessary. This evaluation will occur one time at baseline and one time post-training. Time to administer 30-40 minutes.

Telerehabilitation Study Satisfaction Surveys (Home-based Tele rehabilitation Group and Clinic-based Group) :

Home-based Telerehabilitation Group: This is a 17 question survey of participant satisfaction with the telerehabilitation format. 10 questions use a 5-point Likert scale to address ease of use, convenience, understanding of information provided and general satisfaction. There are 6 open-ended questions for participant comments. Time to administer is approximately 10 minutes.

Clinic-based Group: This is an 12 question survey of participant satisfaction with the clinic-based training format. 5 questions use a 5-point Likert scale to address ease of use, convenience, understanding of information provided and general satisfaction. There are 6 open-ended questions for participant comments. Time to administer is approximately 5-10 minutes.

Home Activity Questionnaire (for Delayed-Entry group only): This is a 10 question survey of activities completed in the week that incorporated the affected arm. Also to record general household activities and community outings. Time to administer is approximately 5 minutes.

MyHealtheVet Training (for the home group only): Training and education about registration and use of MyHealtheVet secure messaging to communicate with the study team will be completed if randomized to the home group. This will take approximately 15 minutes.

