3 * Describe the timing and distribution plan for the payment/reimbursement (schedule, means, etc.)?

The VA requires that we issue vouchers for participants to redeem at the VA cashier's office. Vouchers will be issued from the study team at the Baltimore VA Annex to be redeemed by the participant at the Baltimore VA Medical Center cashiers office at [name]. Reimbursement is \$10 for each study visit completed at the VA. In the event a participant does not complete the study, he/she will receive \$10 per VA visit up until the last day of participation. Payment is as follows:

1) Baseline-At the completion of the entire baseline testing phase, a voucher for the consent and baseline evaluation visits 1-4 and the robot evaluation visit 5 will be issued in the amount of \$50.

2) Final Evaluations-At the retention visit a voucher for the final arm and final robot evaluation and retention evaluation visits will be issued in the amount of \$30.

3) Study Interventions

-If the participant is randomized to the clinic-based rehabilitation group, he/she will receive vouchers for travel to/from the VA for intervention visits 1-18. This will be issued at the final training evaluation visit in the amount of \$180 if all appointments are kept.

-If the participant is randomized to the home-based telerehabilitation group he/she will NOT NEED TO TRAVEL to the VA for intervention visits so will NOT be reimbursed for sessions 1-18.

In summary, if a participant is immediately enrolled in the clinic-based group and keeps all appointments he/she will receive \$260. If a participant is immediately enrolled in the home-based group and keeps all the evaluation appointments he/she will receive \$80. If a participant is in the delayed intervention group, he/she will receive payment for their delayed randomized intervention described above and one additional evaluation reimbursement of \$10 for their delayed retention evaluation.

4 * Method(s) of payment/reimbursement to be Used:

- Cash
- Check
- Money Order
- Gift Certificate/Gift Card
- Other

4.1 If Other, specify:

Vouchers for redemption at the Baltimore VA cashier desk.

HIPAA (Health Insurance Portability and Accountability Act)

- 1 * HIPAA applies to the University of Maryland School of Medicine, the University of Maryland School of Dentistry and the VA. Are you affiliated with, or will be accessing data from, any of these places? Yes No

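### The session voucher goes only to clinic-trained participants and is issued at the post-training evaluation, so it can reveal the lab arm at the visit where the blinded evaluator scores the WMFT

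*Combined protocol and SAP*

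**What the plan says.** **Payment.** Payment/Reimbursement Detail, item 3, sets the calendar.

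- Baseline visits are paid when baseline testing ends ($50).
- Later evaluations are paid together: "At the retention visit a voucher for the final arm and final robot evaluation and retention evaluation visits will be issued" ($30).
- For the clinic-based group, "he/she will receive vouchers for travel to/from the VA for intervention visits 1-18", and the timing is explicit: "This will be issued at the final training evaluation visit in the amount of" $180 if all sessions are kept.
- Home participants do not travel for intervention "visits so will NOT be reimbursed for sessions 1-18".
- For the delayed-entry group, "he/she will receive payment for their delayed randomized intervention described above and one additional evaluation reimbursement" of $10, which the text attaches to the delayed retention evaluation.
- On who hands vouchers over, the section says only: "Vouchers will be issued from the study team at the Baltimore VA Annex".

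**Assessment.** Of the arm evaluations, Study Procedures, item 1, B, says: "These will be performed at the VA by an evaluator blinded to treatment allocation". They take place at baseline, at the end of training (week 6-9) and after the 8-week retention period. The research design section places them at the VA Annex. The WMFT change from baseline to the post-training evaluation is the outcome for both Aim 1 and Aim 2 (Sample Size and Data Analysis, item 2).

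**Blinding safeguard.** The facilities description puts training in a different wing from screening and consent, in order to protect the evaluator's blinding. It does not mention vouchers.

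**The concern.** The trial is single blind, so protection against assessment bias rests on the evaluator not knowing the allocation. The plan separates rooms for this purpose. The payment rule then places an event that only lab-trained participants experience at the visit where the post-training WMFT is scored.

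If the evaluator learns who trained in the clinic, scoring could shift in either direction between lab and home. Aim 2 is decided by whether a confidence bound clears a margin, and the plan already acknowledges that it is under-powered. A shift against home would cost power. A shift in favour of home would make a false declaration of non-inferiority more likely. Knowledge gained at this visit could also carry into the retention scoring.

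**Working it through.** **1. Who receives a voucher at the post-training evaluation?** At $10 per visit:

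- Baseline: 5 × 10 = $50. Final arm, final robot and retention: 3 × 10 = $30. Sessions: 18 × 10 = $180.
- Clinic total: 50 + 30 + 180 = $260. Home total: 50 + 30 = $80. Both match the stated totals.
- Delayed entry, later clinic: 260 + 10 = $270, the stated maximum.

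| Participant | Session voucher at the evaluation |
|---|---|
| Clinic, immediate | $180 |
| Clinic, after delayed entry (post-training) | $180 |
| Home | $0 |
| Delayed entry, end of control period | $0 |

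Because the $30 evaluation voucher is held until retention, no other voucher is scheduled at this visit to mask the $180 one. Its presence therefore identifies lab training. Its absence rules out lab but does not tell home from usual care.

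**2. Which comparison is exposed?** Aim 1 compares home ($0) with delayed-entry usual care ($0), so the voucher does not separate them. Aim 2 compares home ($0) with lab ($180), so it does. The planned Aim 2 size is 33 per group: 22 plus 11 from delayed entry.

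**3. Reproducing the plan's Aim 2 power.** Inputs from Sample Size and Data Analysis, item 1: SD 7.6, n = 33 per group, margin 4.5, one-sided α = 0.025, arms truly equal. The decision rule is the one in item 2: declare non-inferiority if the upper 95% bound is below 4.5.

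- SE = 7.6 × √(2/33) = 1.871; df = 64; critical t = 1.998.
- Noncentrality = 4.5 / 1.871 = 2.405.
- Power from the noncentral t = 65.9%, against 66% stated.

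**4. Illustration with assumed scoring shifts.** The documents give no figure for evaluator bias. Let b be an assumed average difference in scoring between the two arms, in seconds.

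- Favouring lab, arms truly equal: noncentrality = (4.5 − b) / 1.871.
- Favouring home, true difference exactly at the margin: noncentrality = b / 1.871.

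| b (s, assumed) | Power, shift favours lab | One-sided error at margin, shift favours home |
|---|---|---|
| 0 | 65.9% | 2.5% |
| 0.5 | 55.8% | 4.5% |
| 1 | 45.3% | 7.6% |
| 2 | 26.0% | 18.2% |

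**The case against.** The strongest reply is that a payment section gives amounts and timing, not choreography. Another team member could hand over the voucher after scoring, and the plan states twice that the evaluator is blinded. This stands as a limit. A reader might infer that the evaluator is unblinded, but the documents show only that a revealing event is scheduled at the visit. They also contain nothing that keeps the evaluator away from it or places it after scoring.

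A reader might infer that the primary result is at risk, since the WMFT at this visit is the primary outcome. The documents do not support that: neither Aim 1 group receives a voucher at its evaluation.

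A reader might add the arm-specific forms, "Telerehabilitation Study Satisfaction Surveys (Home-based Tele rehabilitation Group and Clinic-based Group"), as a second leak. The plan does not say who gives them or when. They sit in a list that also contains training for the home group only and a questionnaire for the delayed-entry group only, so appearing there does not imply delivery by the evaluator. That is a silence, not a stated rule, and it is not part of this point.

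Finally, the shifts are assumed averages across a whole arm, and the plan describes the WMFT as having high inter-rater reliability. That is a fair reason not to treat the table as a forecast. It does not remove the case for correcting the timing.

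**Conclusion.** The point holds as a cheap improvement. On the written schedule, a voucher at the post-training evaluation identifies a lab-trained participant, at the visit where the blinded evaluator scores the WMFT. The separate training wing is the only concrete safeguard found, and it does not cover this event.

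The exposure is confined to the secondary home-versus-lab comparison. If the evaluator did learn the allocation and scoring moved by an average of 0.5 or 1 s, Aim 2 power would fall from 66% to 56% or 45% (favouring lab), or the one-sided error at the margin would rise from 2.5% to about 4.5% or 7.6% (favouring home). These figures rest on the plan's SD, group size and margin and on shift sizes that are assumed. They show sensitivity, not an estimate of bias.

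One related matter needs reconciling. The Delayed Entry Usual Care paragraph names two lab-based options for the delayed group's later training, whereas the opening of the design section and the recruitment hand-out describe assignment to either the home or the clinic intervention. This affects which delayed-entry participants would receive a session voucher, but not the finding.

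**What to change.** Amend Payment/Reimbursement Detail, item 3, so that training staff, not the evaluator, issue the clinic-session voucher at the last training session, before and apart from the evaluation visit.

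This is preferable to moving the voucher to the retention visit. That would delay travel reimbursement by about eight weeks, and the retention visit is itself a blinded assessment.

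The cost is a small administrative change to the IRB-approved payment plan. Amounts, visits and sample size stay as they are.
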